## **9.2        Adverse events and serious adverse events**

Planned time points for AE and SAE reporting are provided in the Schedules of Activities for Part A (Table 1-4), Part A1 (Table 1-5 and Table 1-6), Part B (Table 1-7), and Part C (Table 1-8). Reporting of AEs and SAEs for Parts D, E, F, and G will be described in a protocol amendment.

The definitions of an AE or SAE can be found in Appendix 3 (Section 11.3).

Adverse events will be reported by the participant (or, when appropriate, by a caregiver, surrogate, or the participant's legally authorized representative).

The investigator, study physician, or medically qualified designee are responsible for detecting, documenting, and recording events that meet the definition of an AE or SAE and remain responsible for following up AEs that are serious, considered related to the study treatment (UCB6114, TFD/TPI [Part B], any individual component of mFOLFOX6 [Part C], or more than 1 of the treatments) or study procedures, or that caused the participant to discontinue the study treatment or study (see Section 7).

All non-serious events of COVID-19 or associated with COVID-19 should be reported as either “suspected COVID-19” or “confirmed COVID-19” utilizing the standard AE form. If additional assessments (e.g. additional labs) are performed by the site, they should be reported on unscheduled visit CRF pages per standard practice.

All serious events of COVID-19 or associated with COVID-19 should be reported as either “suspected COVID-19” or “confirmed COVID-19”, along with additional relevant data, to UCB Patient Safety utilizing the electronic SAE form and in accordance to the timelines outlined within the protocol.

### **9.2.1 Time period and frequency for collecting AE and SAE information**

All AEs and SAEs will be collected from the signing of the ICF until the follow-up visit at the time points specified in the Schedules of Activities for Part A ([Table 1-4](#)), Part A1 ([Table 1-5](#) and [Table 1-6](#)), Part B ([Table 1-7](#)), and Part C ([Table 1-8](#)).

In order to ensure complete safety data collection, all AEs occurring during the study (ie, after the signing of the ICF), including any pretreatment and posttreatment periods required by the protocol, must be reported in the eCRF even if no study medication was taken but specific study procedures were conducted. This includes all AEs not present prior to the initial visit and all AEs that recurred or worsened after the initial visit.

All SAEs will be recorded and reported to the Sponsor or designee within 24 hours, as indicated in Appendix 3 (Section [11.3](#)). The investigator will submit any updated SAE data to the Sponsor within 24 hours of it being available.

The investigator is specifically requested to collect and report to UCB (or its representative) any SAEs (even if the investigator is certain that they are in no way associated with the study medication), up to the Safety Follow-up Visit for each participant, and to also inform participants of the need to inform the investigator of any SAE within this period. Serious AEs that the investigator thinks may be associated with the study medication must be reported to UCB regardless of the time between the event and the end of the study.

The method of recording, evaluating, and assessing causality of AE and SAE and the procedures for completing and transmitting SAE reports are provided in Appendix 3 (Section [11.3](#)).

### **9.2.2 Method of detecting AEs and SAEs**

Care will be taken not to introduce bias when detecting AEs and/or SAEs. Open-ended and non-leading verbal questioning of the participant is the preferred method to inquire about AE occurrences.

### **9.2.3 Follow-up of AEs and SAEs**

After the initial AE/SAE report, the investigator is required to proactively follow each participant at subsequent visits/contacts. All SAEs and non-serious AEs of special interest (as defined in Section [9.2.6](#) and Section [9.2.7](#), respectively), will be followed until resolution, stabilization, the investigator determines that it is no longer clinically significant, the event is otherwise explained, or the participant is lost to follow-up (as defined in Section [7.3](#)). Further information on follow-up procedures for AEs and SAEs is given in Appendix 3 (Section [11.3](#)).

#### **9.2.4 Regulatory reporting requirements for SAEs**

Prompt notification by the investigator to the Sponsor of an SAE is essential so that legal obligations and ethical responsibilities towards the safety of participants and the safety of a study treatment under clinical investigation are met.

The Sponsor has a legal responsibility to notify both the local regulatory authority and other regulatory agencies about the safety of a study treatment under clinical investigation. The Sponsor will comply with country-specific regulatory requirements relating to safety reporting to the regulatory authority, IRB/IEC, and investigators.

Investigator safety reports must be prepared for suspected unexpected serious adverse reactions according to local regulatory requirements and Sponsor policy and forwarded to investigators as necessary.

An investigator who receives an investigator safety report describing a SAE or other specific safety information (eg, summary or listing of SAEs) from the Sponsor will review and then file it along with the IB and will notify the IRB/IEC, if appropriate according to local requirements.

#### **9.2.5 Pregnancy**

Details of all pregnancies in female participants and female partners of male participants will be collected after the start of study treatment and until 3 months after the last study treatment administration.

If a pregnancy is reported, the investigator must immediately inform the Sponsor within 24 hours of learning of the pregnancy and should follow the procedures outlined in Appendix 4 (Section 11.4).

Female participants should be withdrawn from the study as soon as pregnancy is known (by positive pregnancy test), and the following should be completed:

- The participant should return for a Safety Follow-up Visit.
- The participant should immediately stop the intake of the study medication or be down-titrated as instructed at the Safety Follow-up Visit.
- A Final Visit should be scheduled 3 months after the participant has discontinued her study medication.

Abnormal pregnancy outcomes (eg, spontaneous abortion, fetal death, stillbirth, congenital anomalies, ectopic pregnancy) are considered SAEs.

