## Contraception

9. A male participant must agree to use contraception as detailed in Appendix 4 (Section 11.4) of this protocol during the treatment period and for at least 3 months after the last dose of study treatment and refrain from donating sperm during this period.
10. A female participant is eligible to participate if she is not pregnant (see Appendix 4 [Section 11.4]), not breastfeeding, and at least one of the following conditions applies:
  - a. Not a woman of childbearing potential as defined Appendix 4 (Section 11.4).  
OR
  - b. A woman of childbearing potential who agrees to follow the contraceptive guidance in Appendix 4 (Section 11.4) during the treatment period and for at least 3 months after the last dose of study treatment.

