## Contraception

9. A nonsterilized male participant with female partners of reproductive potential must agree to use contraception during the Treatment Period and for at least 6 months after the final dose of study treatment and must refrain from donating sperm during this period.  
A female participant is eligible to participate if she is not pregnant, not breastfeeding, and at least one of the following conditions applies:
  - a. Not a woman of childbearing potential as defined in Appendix 4 (Section 11.4).  
OR
  - b. A woman of childbearing potential who agrees to follow the contraceptive guidance in Appendix 4 (Section 11.4) during the Treatment Period and for at least 6 months after the final dose of study treatment.

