#### **Contraception**

9. A nonsterilized male participant with female partners of reproductive potential must agree to use contraception during the treatment period and for at least 6 months after the final dose of study treatment and must refrain from donating sperm during this period.

A female participant is eligible to participate if she is not pregnant, not breastfeeding, and at least one of the following conditions applies:

- a. Not a woman of childbearing potential as defined in Appendix 4 (Section [11.4](#)).  
OR
- b. A woman of childbearing potential who agrees to follow the contraceptive guidance in Appendix 4 (Section [11.4](#)) during the Treatment Period and for at least 6 months after the final dose of study treatment.

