### Contraception Guidance

#### Male participants

Male participants with female partners of childbearing potential are eligible to participate if they agree to ONE of the following during this study:

- Are abstinent from penile-vaginal intercourse as their usual and preferred lifestyle (abstinent on a long term and persistent basis) and agree to remain abstinent.
- Agree to use a male condom plus partner use of a contraceptive method with a failure rate of <1% per year as described in the table below when having penile-vaginal intercourse with a woman of childbearing potential who is not currently pregnant.

In addition, male participants must refrain from donating sperm for the duration of the study and after the final dose of study medication as follows:

1. For 3 months if participating in Part A or Part A1 of the study;
2. For 6 months if participating in Part B or Part C of the study.

Male participants with a pregnant or breastfeeding partner must agree to remain abstinent from penile-vaginal intercourse or use a male condom during each episode of penile penetration for the duration of the study and, after the final dose of study medication as follows:

1. For 3 months if participating in Part A or Part A1 of the study;
2. For 6 months if participating in Part B or Part C of the study.

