**NOTES:**

- a) Typical use failure rates may differ from those when used consistently and correctly. Use should be consistent with local regulations regarding the use of contraceptive methods for participants participating in clinical studies.
- b) Hormonal contraception may be susceptible to interaction with the study medication, which may reduce the efficacy of the contraceptive method. In this case, 2 highly effective methods of contraception should be utilized during the treatment period and after the final dose of study medication, as follows:
  1. For at least 3 months if participating in Part A or Part A1 of the study;
  2. For at least 6 months if participating in Part B or Part C of the study.

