**Male participants with partners who become pregnant**

- The investigator will attempt to collect pregnancy information on any male participant's female partner who becomes pregnant while the male participant is in this study. This applies only to male participants who receive study medication.
- After obtaining the necessary signed informed consent from the pregnant female partner directly, the investigator will record pregnancy information on the appropriate form and submit it to the Sponsor within 24 hours of learning of the partner's pregnancy. The female partner will also be followed to determine the outcome of the pregnancy. Information on the status of the mother and child will be forwarded to the Sponsor. Generally, the follow-up will be at least 12 months after the delivery date. Any termination of the pregnancy will be reported regardless of fetal status (presence or absence of anomalies) or indication for the procedure.

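### In Parts B and C pregnancies are collected for only 3 months after the last dose, while contraception is required for at least 6 months, so months 4 to 6 have no planned pregnancy record

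*Protocol*

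**What the plan says.** **Collection of pregnancies.** Protocol Section 9.2.5 applies to all parts, and to female participants as well as partners of male participants. Details are "collected after the start of study treatment and until 3 months after the last study treatment administration". Appendix 4 (Section 11.4) ties collection to study participation: for men, it concerns a "female partner who becomes pregnant while the male participant is in this study", and for women, a pregnancy that arises during participation.

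**Contraception, Parts A and A1.** Sections 5.1.1 and 5.1.2 require contraception "during the treatment period and for at least 3 months after the last dose of study treatment".

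**Contraception, Parts B and C.** Sections 5.1.3 and 5.1.4 (criterion 9 in each) require it of women of childbearing potential "during the Treatment Period and for at least 6 months after the final dose of study treatment". Nonsterilized men with female partners of reproductive potential must use it "for at least 6 months after the final dose of study treatment and must refrain from donating sperm during this period". Appendix 4 separates the parts in the same way. For sperm donation, and for men with a pregnant or breastfeeding partner, the period is "For 6 months if participating in Part B or Part C of the study". Where two contraceptive methods are needed, it is "For at least 6 months if participating in Part B or Part C of the study".

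**Last contact.** The schedules for Parts B and C (Tables 1-7 and 1-8) end with the Final Visit, 3 months after the final dose. Section 10.4.1.1 says that survival status is not followed beyond that visit.

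**Reporting that continues afterwards.** Section 9.2.1 keeps serious adverse events (SAEs) that the investigator thinks may be associated with study medication reportable whatever the time elapsed. Appendix 4 makes post-study pregnancy-related SAEs reportable if considered reasonably related, but does not oblige the investigator to look for them.

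**The concern.** The protocol distinguishes the parts when it says how long conception should be avoided, and does not distinguish them when it says how long pregnancies are collected. The two periods agree for monotherapy. For the combinations with TFD/TPI and mFOLFOX6, where the contraception period is twice as long, the collection window stays the same.

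What is at stake is the completeness of the reproductive safety record. Section 9.2.5 classes abnormal pregnancy outcomes as SAEs, and exposed pregnancies with normal outcomes are the denominator needed to interpret them. The protocol itself gives a reason for interest: Sections 2.2 and 2.3 describe ovarian changes in female rats attributed to the mechanism of UCB6114, and Section 4.3.3.1 names reproductive findings in female rats as the possible exception to the absence of toxicity overlapping with cytotoxic chemotherapy.

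**Working it through.** No sample size, power or error rate is involved. The check compares stated periods.

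**Inputs, in months after the last dose**

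| Part | Minimum contraception period (Sections 5.1.1 to 5.1.4) | Pregnancy collection (Section 9.2.5) | Last scheduled contact |
|---|---|---|---|
| A | 3 | 3 | 3 |
| A1 | 3 | 3 | 3 |
| B | 6 | 3 | 3 |
| C | 6 | 3 | 3 |

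**Formula.** Uncovered share = (contraception period − collection window) / contraception period.

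- Parts A and A1: (3 − 3) / 3 = 0%.
- Parts B and C: (6 − 3) / 6 = 3/6 = 50%.

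The contraception period is a minimum, so 50% is the smallest share. It is a share of calendar time, not of expected pregnancies.

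**Does another provision cover months 4 to 6?**

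1. The collection sentences in Appendix 4 depend on being in the study, and the last scheduled contact is at month 3. They add nothing after that.
2. Section 9.2.1 and the post-study sentence in Appendix 4 do reach beyond month 3, but only for SAEs judged related that become known.
3. What remains without planned collection is a pregnancy with a normal outcome, or with an abnormal outcome judged unrelated.

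**Number of participants.** The synopsis allows up to 27 in Part B and up to 27 in Part C: 27 + 27 = 54. This is an enrollment ceiling. The 6-month duty falls only on women of childbearing potential and on nonsterilized men with female partners of reproductive potential. The documents give no figure for that subset, so it lies anywhere from 0 to 54.

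**After the fix.** With a 6-month window in Parts B and C, (6 − 6) / 6 = 0%.

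**The case against.** The best reply has four parts.

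**Related SAEs are still reportable.** A reader might infer that everything in months 4 to 6 goes unrecorded, or that the final safety record must look cleaner than it is. The documents do not support either reading. An abnormal outcome that is judged related and comes to the investigator's attention must be reported under Section 9.2.1 and Appendix 4. This part of the reply stands, and the point is limited accordingly.

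**No text says the two periods must be equal.** This is also true. The 3-month window coincides with the Final Visit, and the protocol does not call the 6 months a risk period. It may be tempting to read the amendment history, where Amendment 4 aligned the Appendix 4 contraception text with the eligibility criteria, as proof of an oversight in Section 9.2.5. The log does not say so, and the point rests on the current text alone. Even so, the protocol gives no reason for matching the periods in Parts A and A1 and not in Parts B and C.

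**Few pregnancies are likely to be involved.** Parts B and C enroll patients with unresectable locally advanced or metastatic gastrointestinal cancer and a required life expectancy of at least 12 weeks. The 54 must not be read as the number able to conceive or father a child. This limits the weight of the point but does not remove the mismatch.

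**Collection to month 6 runs past the Final Visit.** Section 4.4 ends the study at the last participant's last visit, and Appendix 3 takes the electronic tool offline once a site is complete. Reports would therefore be passive, and some would arrive after closure. This stands as a small cost. Appendix 3 already provides a paper or telephone route for SAEs in that situation.

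**Conclusion.** The mismatch is real and confined to Parts B and C. As written, the plan has no planned pregnancy collection for at least 3 of the 6 months in which contraception is required (50% of the minimum period). The gap consists of normal-outcome pregnancies and abnormal outcomes judged unrelated, in an unknown subset of at most 54 participants and in the partners of the men among them. Related SAEs that become known are not lost.

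The conclusion assumes that pregnancy collection is meant to last as long as the contraception requirement, as it does in Parts A and A1. No primary endpoint, dose-escalation decision, sample size or analysis is affected. It is a safety data collection gap worth closing because closing it is cheap.

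**What to change.** Reconcile Section 9.2.5 with the contraception periods as follows.

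1. **Section 9.2.5.** Make the collection window part-specific: until 3 months after the last dose in Parts A and A1, and until 6 months in Parts B and C.
2. **Appendix 4.** Use the same window in the two sentences that govern collection: the first bullet on male participants whose partners become pregnant, and the second bullet on female participants who become pregnant. Leave the first bullet on female participants unchanged, since it concerns study medication and withdrawal rather than data collection.
3. **Final Visit.** Instruct Part B and Part C participants to report any pregnancy, their own or a partner's, up to 6 months after the last dose.
4. **Late reports.** State how a site passes on a pregnancy report once the electronic tool is offline, for example by extending the Appendix 3 paper or telephone route from SAEs to pregnancies.

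The cost is amendment wording, an instruction at a visit that already exists, and a small amount of passive reporting after that visit. No visit or test is added, and the contraception rules and treatment are untouched. Because reporting after month 3 would rely on participants coming forward, the change gives these pregnancies a planned record without guaranteeing complete capture.

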#### **9.2.6 Adverse events of special interest**

An AE of special interest is any AE that a regulatory authority has mandated be reported on an expedited basis, regardless of the seriousness, expectedness, or relatedness of the AE to the administration of a UCB product/compound.

For UCB6114, the following event requires immediate reporting (within 24 hours regardless of seriousness) to UCB:

- Hy's Law
  - Potential Hy's Law, defined as  $\geq 3$ xULN ALT or AST with coexisting  $\geq 2$ xULN total bilirubin in the absence of  $\geq 2$ xULN ALP, with no alternative explanation for the biochemical abnormality (ie, without waiting for any additional etiologic investigations to have been concluded). Follow-up information should be reported if an alternative etiology is identified during investigation and monitoring of the participant.
  - Study participants who have evidence of liver metastases may be considered to have an alternate etiology for the described laboratory abnormalities.

### **9.2.7 Adverse events of special monitoring**

An AE of special monitoring is a product-specific AE, adverse reaction, or safety topic requiring special monitoring by UCB.

For UCB6114, no AEs of special monitoring have been identified.

### **9.2.8 Anticipated serious adverse events**

To date, no humans have been exposed to UCB6114. Thus, no serious AEs with a possible causal relationship to the IMP (ie, suspected serious adverse reactions [SARs]) have been observed in humans. Therefore, all suspected SARs will be considered unexpected and will be reported as such.

Death due to disease progression will not be recorded as a SAE and will be recorded in the survival eCRF. However, if death might be due to other causes, it should be timely reported as a SAE.

### **9.2.9 Infusion-related reactions (hypersensitivity reactions)**

Participants should be observed for at least 6 hours after the start of the first infusion and for 2 hours after the start of the subsequent infusions for symptoms like fever and chills or other infusion-related symptom. Interruption or slowing the rate of the infusion may help control such symptoms. The infusion may be resumed when symptoms abate.

If an infusion-related reaction occurs, the participant must be treated according to the best available medical practice.

Participants should be instructed to report any delayed reactions to the investigator immediately.

Ensure that medications to treat infusion-related reactions, and cardiopulmonary resuscitative equipment are available for immediate use prior to initiation of UCB6114.

In the event of an infusion-related reaction, temporarily stop the drug until resolution, then resume at a reduced infusion rate.

If an infusion is interrupted, it can be restarted if the investigator considers it appropriate to do so. In such instances, the total infusion time may exceed the planned infusion time in order to administer the entire planned dose. The chronology of these events should be recorded accurately

in the source data and eCRF. In addition, the PK sampling times should be adjusted to preserve the relationship of sampling times to the start of the infusion.

If an infusion-related reaction or anaphylaxis occurs, a blood sample will be collected from the study participant as soon as possible, while the event is ongoing, to investigate the nature of the reaction. Evaluation of drug-related hypersensitivity reaction may consist of diagnostic testing and continued monitoring. Further tests may include, but are not limited to cytokine measurements, immunoglobulin E levels, tryptase, complement parameters such as C3a, C5a measurements when there is a suspicion of Type I or III hypersensitivity reaction.

The results of all monitoring, including laboratory testing and other testing, should be made available to the study site and Sponsor.

Premedication to prevent the onset of infusion-related reactions may be allowed for individual study participants based on the Investigator recommendations and after consultation with the Sponsor and should be recorded in the eCRF.

Procedures for reporting infusion-related reactions are the same as those for AEs and SAEs, as described in Appendix 3 (Section 11.3).

